2.1.2 Secondary Objectives

We will also examine possible differences in phototoxicity of the two regimens and assess patient evaluation of treatment. We will additionally assess fluorescence after cream application and before irradiation, using Wood's light as used in routine clinical practice. Efficacy of the two treatment regimens will also be assessed.

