2.2.2. Secondary Outcomes

Phototoxicity as assessed by semi-quantitative scoring of erythema, oedema and urticaria will be assessed immediately after irradiation. Fluorescence will also be assessed after Ameluz and IMP applications using Wood's light. Efficacy of treatment (clearance, partial or no response) three months after PDT will be determined clinically. Patient evaluation of treatment will also be assessed.

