A study clinician, technologist or nurse will obtain a medical history and the areas for treatment will be examined, the study fields will be marked out, lesions counted and the fields mapped and photographed. The maximal diameter of each comparable field will be 5x10cm. Topical PDT will be undertaken using the standard Ameluz[®] PDT regime (11). In brief, any hyperkeratotic areas will be surface prepared using a disposable ring curette (Stiefel[™]), without the need for local anaesthesia. Ameluz[®] gel will be thinly applied to both comparative fields, left to dry and occluded for three hours with Tegaderm and Mepore dressings. After removal of the dressings and surplus gel, the active treatment (menthol 5% in aqueous cream) or placebo (aqueous cream) will be applied to right/left side according to randomisation. The IMPD/placebo will be provided as 1g in 2mL syringes, applied to the maximum field size field of 5x10cm or pro-rata to smaller field sizes. Ten minutes later any excess cream will be wiped off and irradiation will commence (LED 37.5 J/cm², irradiance approximately 80 mW/cm²), with the randomisation to account for which side will be treated first. Menthol vapour will be in the room in order to mask the vapour of the IMP and to aid with ensuring blinding of both patient and assessor (research nurse or another technologist).

Assessments

Fluorescence will be examined using a semi-quantitative scoring system (0=none; 1=minimal; 2=moderate; 3=strong) after 3 h of Ameluz application and after menthol/placebo application.

Pain scores will be recorded by the patient immediately after irradiation (as recall of maximal pain experienced during irradiation) and at 3, 6 and 24 h after irradiation

A randomised double blind, placebo controlled study of the efficacy of topical menthol for pain relief during topical photodynamic therapy

[figure not shown]
v.6.0 27/March/2019

using a VAS score of 0-10cm at each time-point. The study technologist or research nurse will be present at the time of the first pain score but patients will fill in the VAS scores themselves at home for the 3, 6 and 24 h time-points and send these back to the PDT clinic by stamped addressed envelope. A study nurse will contact the patient by phone at one week, to ask about any adverse effects and to check that the VAS scores are returned.

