5.5 RANDOMISATION

5.5.1 Randomisation

Randomisation will be to left or right side within each individual as we cannot consider pain experiences on right vs. left within an individual as being independent. We want to compare pain immediately after PDT illumination (time-point of most interest) and, as another way of comparing between the interventions "pain experience over-time" (while trying to reduce the multiple comparisons "problem"), to compare within-subjects Areas Under the Curve of pain over time.

Patients will be randomly allocated to either active or placebo treatment to right or left side using a computer-generated block randomisation sequence, which will also include randomisation as to which side will be treated first. The randomisation code will be generated by Tayside Pharmaceuticals and will be concealed from study investigators.

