9 STATISTICS AND DATA ANALYSIS

9.1 SAMPLE SIZE CALCULATION

We were not able to obtain variance for within-subjects pain differences from similar studies. An assessment of pain experience with PDT in our unit found a standard deviation of between subjects VAS pain score of 2.7cm. Rounding this up to 3cm and conservatively estimating that within-subject's pain score SD will be two-thirds of this (2cm) then we estimated that 21 subjects should give us 90% power to detect a mean difference in VAS scores of 1.5 cm as significant at the 5% level. To allow for dropouts, assuming dropout rate by 3 months of up to 30%, we will recruit 30 subjects.

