9.2 PROPOSED ANALYSES

The main analysis will be the difference between within-subject pain using appropriate paired methods (paired Student's t-test if assumptions met). The difference will be expressed with 95% confidence interval. VAS scores immediately after PDT and the areas under the curve for pain scores plotted over each of the time points will be assessed. Within subject comparisons of fluorescence, phototoxicity, efficacy and patient evaluation will be secondary outcome measures, using paired statistical analyses.

Amendment

Since the original concept and set up of the study, there have been changes in the practice of PDT for AKs on the face and scalp, with low illuminance daylight PDT now favoured when practicable because this form of PDT is less painful than conventional PDT. Therefore, we will perform (statistical analysis by someone not involved in patient treatments and assessments, to ensure blinding) an interim analysis. With the same assumptions as before with a power of 90% we expect to detect a difference (at alpha = 0.1 level, two tailed testing) of 3 cm or more (on VAS) in pain between groups with 9 subjects should such a difference exist. We will therefore recruit a minimum of 9 participants and if on this interim analysis such a difference is detected then the study will be continued as originally planned in order to determine whether the difference can be detected at alpha = 0.05 level of significance, unless the dermatologist analysing the data advises stopping early as a greater difference already detected. If it seems unlikely that there will be a difference of ≥ 3 cm in pain

A randomised double blind, placebo controlled study of the efficacy of topical menthol for pain relief during topical photodynamic therapy

v.6.0 27/March/2019

on VAS based on this interim analysis, then (with the changes in use of PDT for AKs on face and scalp) the data analyst will advise stopping the study.

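### Section 9.2 gives the pre-cream fluorescence score no role; adjusting the post-cream side comparison for it would cost nothing to collect and could improve precision

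*Combined protocol and SAP*

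**What the plan says.** Section 3.1 (Assessments) scores fluorescence on a four-level scale from 0 to 3, "after 3 h of Ameluz application and after menthol/placebo application". Section 2.2.2 also names both occasions: "Fluorescence will also be assessed after Ameluz and IMP applications". The objective in section 2.1.2 is narrower: "We will additionally assess fluorescence after cream application and before irradiation". The opening summary words it in the same way.

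For analysis, section 9.2 offers one sentence covering four secondary outcomes: "Within subject comparisons of fluorescence, phototoxicity, efficacy and patient evaluation will be secondary outcome measures, using paired statistical analyses". A paired t-test is named only for pain. For fluorescence no occasion, change score, adjustment or test is stated.

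On allocation, section 5.5.1 says: "Randomisation will be to left or right side within each individual".

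**The concern.** Pairing removes differences between patients. It does not remove differences between the two fields of one patient, such as lesion load, surface preparation or Ameluz uptake. Any such difference in photosensitiser signal before the cream carries into the post-cream side difference. The pre-cream score measures it on the same field shortly beforehand, yet the plan gives that score no use.

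The comparison has a purpose. Section 1.1 reports that pain appears to follow the rate of PpIX photobleaching, and that menthol left PpIX fluorescence unchanged in mice. The fluorescence comparison is the human counterpart of that check. If it is noisy, a real change in signal can be missed. Post-cream, change and adjusted analyses would all fit the wording of 9.2, so the choice could also be made after the data are seen.

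**Working it through.** **The plan's own figure.** Section 9.1 states that "21 subjects should give us 90% power to detect a mean difference in VAS scores of 1.5 cm as significant at the 5% level". Taking its 2 cm as the SD of the paired difference and the 5% level as two-sided, a paired t-test (noncentral t) gives power 0.905 at n = 21 and 0.889 at n = 20, so 21 reproduces. Dropout: 21 / (1 - 0.30) = 30. This figure concerns pain; no figure is stated for fluorescence.

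**How many patients apply.** The 30% loss is by three months. The study matrix (3.3) puts fluorescence on Day 1, so up to 30 patients could contribute, or about 9 if the study stops at the interim analysis in 9.2.

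**Chance imbalance.** The standard error of the mean pre-cream side difference is SD / √n. The SD is assumed, over 0.5 to 1.0 points:
- n = 9: 0.5/3 = 0.17 to 1.0/3 = 0.33
- n = 21: 0.5/4.58 = 0.11 to 1.0/4.58 = 0.22
- n = 30: 0.5/5.48 = 0.09 to 1.0/5.48 = 0.18

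**Variance relative to post-cream only.** Let r be the correlation between pre- and post-cream side differences, with equal variances. The change score has relative variance 2(1 - r). The adjusted comparison has 1 - r², before the small cost of estimating a slope.

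| r | Change | Adjusted |
|---|---|---|
| 0.3 | 1.40 | 0.91 |
| 0.5 | 1.00 | 0.75 |
| 0.7 | 0.60 | 0.51 |
| 0.9 | 0.20 | 0.19 |

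**Is the post-cream comparison biased?** A simulation of a 0-3 score (20,000 runs per setting) randomised side within patient and built in a systematic right-left difference of 0.3 points. With no menthol effect, the mean post-cream estimate was 0.00 and the rejection rate 4.6% to 5.6% across n = 9, 21 and 30. So there is no bias.

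**Power in the same simulation.** Assumed underlying effect -0.4 points, measurement-noise SD 0.3, and three values for the SD of side differences. Each cell gives post-cream only / change / adjusted:

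| SD of side differences | n = 9 | n = 21 | n = 30 |
|---|---|---|---|
| 0.3 | 0.30 / 0.24 / 0.30 | 0.67 / 0.55 / 0.69 | 0.82 / 0.72 / 0.85 |
| 0.6 | 0.23 / 0.24 / 0.26 | 0.50 / 0.55 / 0.62 | 0.66 / 0.71 / 0.79 |
| 0.9 | 0.17 / 0.23 / 0.23 | 0.35 / 0.54 / 0.57 | 0.46 / 0.71 / 0.75 |

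**A second set of assumptions.** Underlying mean 2, patient SD 0.6, scoring-error SD 0.25, menthol shift 0.5, scores rounded and clipped to 0-3, n = 21:
- side SD 0.5 (r about 0.6): post-cream only about 69%, change about 81%, adjusted about 85%
- side SD 0.3 (r about 0.37): 88%, 81%, 91%
- side SD 0.2 (r about 0.2): 94%, 81%, 94%

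At n = 9 with low r, adjustment cost at most about 4 points of power.

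**The case against.** Randomisation already deals with the main worry. A reader might infer that existing side differences bias the fluorescence result or are confounded with menthol. The documents do not support that: side is allocated at random within each patient, so the post-cream difference is right on average, and chance imbalance is sampling error that the 5% test level already covers. This stands, and it limits the point to precision and a plan left open.

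A reader might also infer that 9.2 lays down a post-cream-only analysis. It does not. It is silent on the pre-cream score, section 2.2.2 names both occasions, and a paired analysis of change would fit the wording. This stands too. But silence leaves the choice open, and the summary and 2.1.2 lean towards the post-cream score.

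Finally, the benefit may be small. Nothing in the documents gives a fluorescence SD, correlation or effect size, and a four-level score will produce many tied sides. At low r adjustment gains almost nothing, and with 9 patients it can cost a little. This is fair as to size. At n = 21 and 30, however, the adjusted analysis matched or beat the post-cream comparison at every correlation tried.

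**Conclusion.** The point holds as lost precision and an unstated analysis. The trial collects a baseline for fluorescence and its plan does not say how to use it. With 21 patients the gain in power runs from negligible at r about 0.2 to about 16 points (69% to 85%) at r about 0.6. With about 9 patients and low r, adjustment could cost up to about 4 points. All of these sizes rest on assumed correlations, SDs and effects.

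The raw change score is not an equal substitute: it falls behind the post-cream comparison when r is below 0.5 (94% down to 81% at r about 0.2, n = 21). Fluorescence is a secondary outcome with no power claim, so this is a minor improvement.

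**What to change.** In section 9.2, name one fluorescence analysis. For each patient take menthol side minus placebo side, before and after the study cream. Regress the post-cream difference on the pre-cream difference and test the intercept, which estimates the menthol effect when the sides start equal. Report it with a 95% confidence interval. Because the score is ordinal, add a permutation or sign-flip p-value or similar check; in a sign-flip, reverse a patient's pre- and post-cream differences together. Report the pre-cream side difference descriptively, without a test. Do not list the raw change score as an alternative. Align the wording of the summary and 2.1.2 with 2.2.2 and 3.1.

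The cost is a sentence or two, through the amendment route in section 14.1, and one degree of freedom. Section 3.1 already provides for both scores, so no new visit or measurement is needed. The study matrix has a single fluorescence row, so confirm that the CRF records each side on each occasion.

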2.2 OUTCOMES

2.2.1 Primary Outcomes

Pain will be assessed by the patient using a visual analogue scale of 0-10 cm. Maximal recall of pain experienced during PDT will be recorded immediately after PDT, and then pain scores at three, six and 24 hours after PDT. The patient-scored pain at the first time point will be undertaken with the aid of a blinded investigator and subsequently the patient alone will assess symptoms.

A randomised double blind, placebo controlled study of the efficacy of topical menthol for pain relief during topical photodynamic therapy

v.6.0 27/March/2019

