4 STUDY POPULATION

4.1 NUMBER OF PARTICIPANTS

30 patients will be recruited to the study, with a view to 21 completing the study allowing for a 30% drop-out rate at the three month follow-up visit. The study will be performed in one centre and each participant will be in the study for three months.

A randomised double blind, placebo controlled study of the efficacy of topical menthol for pain relief during topical photodynamic therapy

v.6.0 27/March/2019

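### Does the interim's 90% power with 9 subjects need correcting because the protocol does not say whether 9 is recruited or evaluable, or which SD the 2 cm is?

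*Combined protocol and SAP*

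**What the plan says.** Section 9.1 says that no variance for within-subject pain differences could be found. It takes a between-subject SD of 2.7 cm, rounds it up to 3 cm, and assumes that the within-subject "pain score SD will be two-thirds of this (2cm) then we estimated that 21 subjects should give us 90% power" for a mean difference of 1.5 cm at the 5% level. It then adds a dropout margin: "assuming dropout rate by 3 months of up to 30%, we will recruit 30 subjects". Section 4.1 makes the same separation, 30 recruited with a view to "21 completing the study allowing for a 30% drop-out rate at the three month follow-up visit".

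The amendment in section 9.2 adds an interim analysis. It says "With the same assumptions as before with a power of 90% we expect to detect a difference", at two-tailed alpha 0.10, "of 3 cm or more (on VAS) in pain between groups with 9 subjects should such a difference exist". The next sentence begins "We will therefore recruit a minimum of 9 participants". It gives no separate evaluable count and does not mention dropout.

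On the pain score, section 2.2.1 says: "Maximal recall of pain experienced during PDT will be recorded immediately after PDT, and then pain scores at three, six and 24 hours". Section 3.1 adds that "patients will fill in the VAS scores themselves at home for the 3, 6 and 24 h time-points" and post them back. Section 5.5.1 singles out pain immediately after illumination as the time point of greatest interest, with area under the curve as another way of comparing the treatments. The analysis paragraph of section 9.2 names a paired t-test, if its assumptions hold.

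**The concern.** In section 9.1 the number that carries the power (21) is the evaluable number, and the recruited number (30) is stated separately. In the amendment one number, 9, does both jobs. A reader who carries over the convention of section 9.1 takes 9 as evaluable, and then the stated 90% does not match: 9 evaluable subjects with an SD of 2 cm give 99.3%.

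The wording of the SD adds to the doubt. A paired test needs the SD of the left-right differences, but section 9.1 calls its 2 cm a within-subject pain score SD. If 2 cm is taken as the SD on each side, with independent sides, the difference SD is 2 × √2 = 2.83 cm, and 9 evaluable subjects give 89.5%, which looks like the stated 90%. A reader could settle on the wrong SD and then doubt the main sample size.

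The amendment also says only that the 3 cm is on the VAS and names no time point, so which participants count as evaluable is not spelled out. Because this interim can end the trial, an error in its size would matter.

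**Working it through.** **Inputs.** From section 9.1: SD 2 cm, difference 1.5 cm, alpha 0.05, 90% power, 21 subjects, dropout up to 30%, 30 recruited. From section 9.2: difference 3 cm, two-tailed alpha 0.10, 90% power, 9 subjects, the earlier assumptions carried over, paired t-test. Section 9.1 does not state the sides of its test. Two-sided is assumed here because it reproduces 21; one-sided would need 17.

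**Formula.** For a paired t-test with n pairs, difference δ and difference SD σ, the statistic follows a noncentral t distribution with n − 1 degrees of freedom and noncentrality δ√n/σ. Power is the probability that it falls beyond ±t(1 − α/2; n − 1).

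**Step 1: reproduce the main design (σ = 2, δ = 1.5, two-sided 0.05).**
- n = 20: noncentrality 0.75 × √20 = 3.35, power 88.9%
- n = 21: noncentrality 0.75 × √21 = 3.44, power 90.5%
- Dropout: 21/0.7 = 30

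Both stated figures are recovered, so 2 cm works as the SD of the paired differences.

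**Step 2: interim with the same inputs (σ = 2, δ = 3, two-sided 0.10).**

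| Evaluable | Noncentrality 1.5√n | Power |
|---|---|---|
| 5 | 3.35 | 86.2% |
| 6 | 3.67 | 93.1% |
| 7 | 3.97 | 96.7% |
| 8 | 4.24 | 98.4% |
| 9 | 4.50 | 99.3% |

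Six is the smallest evaluable number that reaches 90%. With the dropout margin of section 9.1, 6/0.7 = 8.57, which rounds up to 9. This follows the same route as 21/0.7 = 30. If all 9 are evaluable, 90% power is reached at a difference of about 2.14 cm.

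**Step 3: other readings that come close to 9.** None of them also gives 90% power with 21.

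| Reading | Power, 9 at the interim | Power, 21 in the main design |
|---|---|---|
| Paired, difference SD 2 cm | 99.3% (6 evaluable: 93.1%) | 90.5% |
| Paired, 2 cm per side (difference SD 2.83 cm) | 89.5% | 63.8% (40 needed) |
| Paired, difference SD 2.7 cm | 91.8% | 67.8% |
| Paired, difference SD 3 cm | 86.2% | 58.7% |
| Two independent groups, SD 2 cm, n per group | 91.9% | 66.0% |

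Only a difference SD of 2 cm, with 9 as the number recruited after dropout, fits both stated figures.

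**Step 4: if 9 are recruited and some are lost.** Let the number evaluable be Binomial(9, 1 − loss) and average the power over it. The loss rates are assumptions; the protocol gives only the ceiling of 30% by three months.

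| Loss | Average power |
|---|---|
| 5% | 98.8% |
| 10% | 98.1% |
| 20% | 95.7% |
| 30% | 91.3% |

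The low end of the loss range is the realistic one if the interim uses the immediate score, which is recorded in clinic on Day 1 with staff present. Dropout at a three-month visit says little about that score.

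**The case for a change.** The strongest case for a change is that an interim able to stop the trial should state its own terms. The power sentence ties 90% to 9 subjects, the evaluable 6 appears nowhere, and a reader has to work backwards to find it. Carrying over the earlier assumptions may include dropout, but that dropout belongs to the three-month visit, not to a pain score. The amendment names no time point, and a participant whose posted scores are missing could count for the immediate score but not for the area under the curve. Fewer than 6 evaluable is also possible: with 5, power is 86.2%.

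The omissions stand as matters of drafting. Their consequences are limited:

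- The sentence after the power statement recruits at least 9. That labels 9 as a recruitment number and as a minimum, so losses can be made up.
- Section 9.1 opens by naming the variance of within-subject differences as the missing quantity and then supplies 2 cm in its place. With the paired test in section 9.2, that identifies the SD, and the figure of 21 confirms it.
- A criterion of 3 cm on the VAS is a score, not an area under the curve, and section 5.5.1 gives priority to the immediate score. For the scores completed at home, section 3.1 provides a one-week telephone call to check that they are returned.
- A result as low as 5 evaluable would take a loss of 4 in 9, which is unlikely for a score taken in clinic. Even at 30% loss, average power stays above 90%.

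**Conclusion.** No change follows. These are gaps that an analyst fills from the surrounding text, and the stated numbers agree with one another: 21 evaluable and 30 recruited for the main design, 6 evaluable and 9 recruited for the interim. Under the plan's SD, power for 3 cm is 93.1% with 6 evaluable, 99.3% with 9, and 91.3% on average at 30% random loss. Added labels would give the same interim on the same participants with the same test and decision rule.

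This rests on 2 cm being the SD of the paired differences, on a two-sided main test, and on losses being random. It concerns only whether the stated figures agree. It does not show that 2 cm is the true SD; if the difference SD were 3 cm, 9 evaluable subjects would give 86.2%. How the authors arrived at 9 is not documented. The dropout route is inferred because it is the only one examined that fits both designs.

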3.3 STUDY MATRIX

| ACTIVITY | Day 1 | Day 2 | DAY 8 | Approx. 3 months |
|--|-------|-------|-------|------------------|
| Informed consent | √ | | | |
| Eligibility screening | √ | | | |
| Standard skin preparation for PDT | √ | | | |
| Application of IMP/placebo (remove after 10 minutes) | √ | | | |
| PDT irradiation | √ | | | |
| Pain assessment (visual analogue scores) by subject immediately after PDT - clinic | √ | | | |
| Fluorescence assessment by technician | √ | | | |
| Phototoxicity assessment by technician | √ | | | |
| Pain assessment (visual analogue scores) by subject 3hrs after PDT - home | √ | | | |
| Pain assessment (visual analogue scores) by subject 6 hrs after PDT - home | √ | | | |
| Pain assessment (visual analogue scores) by subject 24 hrs after PDT - home | | √ | | |
| Follow-up phone call by research nurse | | | √ | |
| Assessment of treatment efficacy at 3 months after PDT | | | | √ |
| Patient evaluation of PDT & blinding | | √ | | |

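### The 90% power for 1.5 cm in section 9.1 takes no account of the 9.2 amendment's advice to stop at an interim from 9 patients, and that advice has no numerical threshold

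*Combined protocol and SAP*

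**What the plan says.** Section 9.1 assumes a within-subject SD of 2 cm and states that "21 subjects should give us 90% power to detect a mean difference in VAS scores of 1.5 cm as significant at the 5% level". It recruits 30 to allow for up to 30% dropout by three months.

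The amendment in section 9.2 explains that daylight PDT, which hurts less, is now preferred where practicable, and adds an interim analysis at a minimum of 9 participants. Its basis carries over from 9.1: "With the same assumptions as before with a power of 90% we expect to detect a difference". The test, effect size and sample size attached to that claim read "at alpha = 0.1 level, two tailed testing) of 3 cm or more (on VAS) in pain between groups with 9 subjects". Two sentences then govern the decision:

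- Continue: "if on this interim analysis such a difference is detected then the study will be continued as originally planned", with final testing at 0.05.
- Stop: "If it seems unlikely that there will be a difference of ≥ 3 cm in pain". In that case, says the plan, "the data analyst will advise stopping the study".

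For the main analysis 9.2 also says "The difference will be expressed with 95% confidence interval". Section 9.1 does not mention the interim.

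**The concern.** Both sections are current text in v6.0. Section 9.1 sizes the trial for 1.5 cm, while the interim asks about a difference twice as large. A menthol effect of 1.5 cm, the one 9.1 says the trial can find, may well fail to show itself as 3 cm in nine patients. If the advice is followed, some trials with a real 1.5 cm benefit stop there, and the 90% no longer describes the trial.

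The decision also cannot be reproduced. The continue sentence has a nominal test behind it (two-tailed alpha 0.10), but the stop sentence has no number.

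At stake is how a stopped trial is read. Beside an unrevised 90%, a stop at nine could be taken as good evidence against 1.5 cm.

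**Working it through.** **Inputs.** From 9.1: SD 2 cm, difference 1.5 cm, 5% level, 21 subjects, 30 recruited. From 9.2: paired t-test, interim at 9, two-tailed alpha 0.10, 3 cm. Assumptions made here: 2 cm is the SD of the paired differences (the value that reproduces 21); the 5% test is two-sided; differences are normal; the stop advice is followed.

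Final sizes of 21 and 30 are both shown. The immediate score is a Day 1 item in section 3.3 ("Pain assessment (visual analogue scores) by subject immediately after PDT - clinic"), whereas the 30% dropout applies by three months.

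**Formula.** Power = P(T > t(1−α/2, n−1)), where T is noncentral t with n−1 df and noncentrality δ√n/SD.

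**Step 1: the plan's own figure.** n = 21: noncentrality 1.5 × √21 / 2 = 3.44, critical value 2.086, power 90.5%. It reproduces, and 21 is the smallest n reaching 90%. With n = 30 power is 97.8%. Neither figure includes an interim.

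**Step 2: chance of passing the interim at a true 1.5 cm.** n = 9, alpha 0.10: noncentrality 1.5 × 3 / 2 = 2.25, critical value 1.860, probability 65.9%. On the p<0.10 reading this caps overall power, whatever the final sample and whether or not the discretionary early stop for a large effect is used.

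**Step 3: overall power at a true 1.5 cm.** Simulation with the interim patients nested in the final sample, each trial using its own SD, at least 400,000 trials per scenario. Success is final two-sided p<0.05 favouring menthol after continuing.

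| Continue at n = 9 if | Final n 21 | Final n 30 |
|---|---|---|
| No interim | 90.5% | 97.8% |
| Two-tailed p<0.10 favouring menthol | 64.0% | 65.5% |
| Observed mean at least 3 cm | 1% | 1% |
| Upper 90% limit reaches 3 cm | 33% | 34% |
| Upper 95% limit reaches 3 cm | 47% | 49% |
| p<0.10, or 3 cm inside the 95% CI | 71% | 73% |
| p<0.10, or 3 cm inside the 99% CI | 81% | 86% |

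On the p<0.10 rule with a final n of 21, power is 86% at a true 2 cm and 99% at 3 cm; it reaches 90% at about 2.15 cm. Nine is a minimum, so later looks matter. On the same rule power at 1.5 cm (final n 21; 30) is 76%; 78% at 12 patients, 84%; 86% at 15, and 89%; 91% at 18.

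**Step 4: the stopped trials.** Of trials stopped on the p<0.10 rule at a true 1.5 cm, 93% have an interim 95% CI that still includes 1.5 cm.

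**Step 5: the missing threshold.** With an observed SD of 2 cm and n = 9, the 90% CI half-width is 1.860 × 2 / 3 = 1.24 cm. A mean above 1.24 cm gives p<0.10. A mean below 3 − 1.24 = 1.76 cm puts 3 cm outside the 90% CI. If improbable is read through that interval, any mean from 1.24 to 1.76 cm satisfies both the continue and the stop sentence.

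**Step 6: the nine subjects.** At SD 2 cm, 3 cm and alpha 0.10, power is 86.2% with 5 subjects, 93.1% with 6 and 99.3% with 9. Six are enough. With 9.1's dropout, 6 / 0.70 = 8.6, so 9 recruited.

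**The case against.** The strongest reply is that the stop is advice, that nine is a minimum, and that the amendment gives the interim its own n, alpha, power and difference and explains the change. A higher bar for a declining indication is the sponsor's choice. All of this stands. It means 64% is conditional and is not the power of the trial: with no threshold in the text, no single figure can be. It does not rescue the 90%, which is still stated for 1.5 cm with no word that it excludes the interim.

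The 3 cm criterion also belongs to the plan, so p<0.10 alone is one reading of the continue rule. The readings that require the 3 cm criterion alone to be met, at 1% to 47% in the table, give less power.

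Four stronger inferences are tempting, and the documents do not support them:

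- *No interim of this kind can keep 90%.* A p<0.10 look at 18 patients with 30 final gives about 91%.
- *The nine subjects expose a different SD or an unpaired calculation, so the trial is underpowered throughout.* Nine would fit an SD of differences near 2.8 cm or an unpaired test. But 9.1 states 2 cm, that value reproduces 21, and six inflated for 30% dropout also gives nine. The amendment does not state that route, so it is plausible rather than shown; either way nine is more than enough at 2 cm.
- *Stopping for lack of effect inflates the false-positive rate.* It lowers it: about 2% two-sided on the p<0.10 rule with 21 final subjects.
- *Readers will credit a stopped trial with 90% power.* That is a risk, not a certainty. Section 9.2 does ask for a 95% CI in the main analysis, but it does not say that an interim stop must be reported with one.

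**Conclusion.** The point holds as an uncorrected power statement and an undefined rule, and should be fixed. At SD 2 cm, 9.1's 90% for 1.5 cm is right only if the interim does not stop the trial. With the advice followed at exactly nine patients, power is about 64% to 66% on the p<0.10 reading and between 1% and 86% across the readings tried; none of these reaches 90%. A later look narrows the loss on the p<0.10 rule and by 18 patients nearly removes it against the stated 90%. Because the stop sentence has no threshold, the same nine patients can lead to opposite advice.

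The mismatch over nine subjects is minor: nine analysed subjects give 99% power for 3 cm, not 90%. It is harmless at SD 2 cm and needs only clarification.

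**What to change.** 1. The sponsor states whether the target is still 1.5 cm or is now 3 cm, and whether the stop is binding.
2. Replace the stop wording with one numerical rule, at a stated interim size, that is the complement of the continue rule. Options are p<0.10 favouring menthol; a CI rule against 3 cm; or, if 1.5 cm remains the target, stopping only when the upper 90% limit is below 1.5 cm (about 87% power with 21 final subjects, 93% with 30).
3. Restate the power in 9.1 under the chosen rule. For p<0.10 at n = 9 with 21 final subjects and SD 2 cm: about 64% at 1.5 cm, 86% at 2 cm and 99% at 3 cm. If the target is now 3 cm, say that the 90% for 1.5 cm no longer applies.
4. In 9.2, state that nine analysed subjects give about 99% power for 3 cm at SD 2 cm, or that nine includes dropout.
5. If the trial stops at the interim, report the mean difference with its 95% CI and say that the stop does not by itself exclude a 1.5 cm benefit.

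**Cost.** A less favourable stated power; no added patients or procedures, unless the 1.5 cm rule is chosen. That rule stops less often: with no true effect 66% of trials stop, against 95% on p<0.10. Expected enrolment with no effect then rises from 9 + 0.05 × 12 = 9.6 to 9 + 0.34 × 12 = 13.1 (maximum 21), or from 9 + 0.05 × 21 = 10 to 9 + 0.34 × 21 = 16 (maximum 30).
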